9.1.3 Dosage and Administration

The study products will be injected by suitably trained clinical staff. The covered syringes containing IFN-K and placebo will be indistinguishable. Please refer to the Pharmacy Manual provided separately.

Administration methods of IFN-K and placebo throughout the study are outlined in Table 3:

1- Each patient will receive two injections of study product (corresponding to 240 mcg of IFN-K or placebo) at 3 visits during the induction period (at Week 0 [visit 2], Week 1 [visit 3] and Week 4 [visit 4]).

2- Each patient will then be administered one injection of study product (corresponding to 120 mcg of IFN-K or placebo) at 2 visits during the maintenance period (at Week 12 [visit 6], Week 24 [visit 9]).

The duration of this intermittent study treatment will be 24 weeks from the first (Week 0 [visit 2]) to the last administration (Week 24 [visit 9]).

The study drug will be administered by intramuscular route in various body muscles (deltoid, buttock or thigh muscles) as displayed in the Table 3, to minimize the injection site reactions. Patients will be required to stay in the clinic for 1 hour post-dose for evaluation of any adverse reactions/events (see Section 11.2).

Table 3 Dosage and Administration of Study Products

Visit	Study Week	Injection	Groups IFN-K	Group Placebo	Study product	Route	Site	Side
2	Week 0	1	IFN-K		IFN-K 240 mcg + ISA 51 VG	IM	D	R/L
				Placebo	Sodium Chloride solution + ISA 51 VG	IM	D	R/L
3	Week 1	2	IFN-K		IFN-K 240 mcg + ISA 51 VG	IM	B	R/L
				Placebo	Sodium Chloride solution + ISA 51 VG	IM	B	R/L
4	Week 4	3	IFN-K		IFN-K 240 mcg + ISA 51 VG	IM	T	R/L
				Placebo	Sodium Chloride solution + ISA 51 VG	IM	T	R/L
6	Week 12	Booster 1	IFN-K		IFN-K 120 mcg + ISA 51 VG	IM	D	L
				Placebo	Sodium Chloride solution + ISA 51 VG			
9	Week 24	Booster 2	IFN-K		IFN-K 120 mcg + ISA 51 VG	IM	D	R
				Placebo	Sodium Chloride solution + ISA 51 VG			

D = deltoid muscles B = buttock muscles; T = thigh muscles; IFN-K = interferon-kinoid; IM = intramuscular; R/L = Right / Left;

9.2 Treatment Allocation and Randomization

A total of 166 patients will be enrolled in the study and randomly assigned into each cohort sequentially in a 1:1 ratio between the IFN-K group and the placebo group as described in Section 9.2.2.

Randomized patients who do not receive any study product will not be replaced and will be handled as drop-out patients (see Section 13.6).

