	
– The Systemic Lupus International Collaborating Clinics/American College of Rheumatology-Damage Index for Systemic Lupus Erythematosus (SLICC/ACR DI)– The Cutaneous Lupus Erythematosus Disease Area and Severity Index (CLASI) in patients with cutaneous lesions at baseline• To evaluate the immune response induced by IFN-K
– Anti-IFNα antibody response– Anti-Keyhole Limpet Hemocyanin (KLH) antibody response– Anti-IFNα antibody neutralizing capacities• To assess the safety of IFN-K emulsified with ISA 51 VG 
Exploratory Objectives
 
The exploratory objectives of this study are:
 
• To assess disease activity using:
– The Physician's Global Assessment (PGA) score– The 28-Tender and Swollen joint counts– A Joint Pain Visual Analog Scale (VAS)– The flare description– The changes in Lupus therapy• To assess quality of life using:
– The Short Form (SF)-36 questionnaire– The Functional Assessment of Chronic Illness Therapy (FACIT) fatigue score• To assess biological parameters:
– Levels of lupus related serum auto-antibodies and biomarkers– Neutralizing capacity against IFNα subtypes– Anti-IFNα and Anti-KLH antibody isotyping– IFNβ cross-neutralization– Antibody response to influenza vaccination• To assess correlations between immune responses, IFN gene signature and clinical responses
Study Design:	
This will be a Phase IIb, randomized, double-blind, placebo-controlled, multicenter study.
 
Study patients will be enrolled into one of the two treatment groups and allocated in a 1:1 randomization ratio to receive IFN-K or placebo as outlined below:
 
• Group 1: IFN-K emulsified in ISA 51 VG• Group 2: placebo emulsified in ISA 51 VG 
A total of 178 patients (89 patients in each group) will be enrolled.
 
The main study is comprised of 12 visits occurring over a period of 40 weeks. The main study will be divided into four periods: a 4-week Screening Period that will be performed to determine eligibility of the patients for randomization into the study, a 12-week Induction Period, a 12-week Maintenance Period and a 12-week Follow-up Period.
 
Study patients will then enter in an Extended Follow-up study period for a duration of additional 240 weeks (60 months).

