8. STUDY POPULATION

8.1 Number of Patients

The target number of eligible patients to be enrolled in this study is 178 (89 patients in each treatment group).

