13.1 Determination of Sample Size

The primary objective of this study is to evaluate the neutralization of the IFN gene signature following treatment with IFN-K, as measured by the change from baseline of the expression of IFN-induced genes **and** to evaluate the efficacy of treatment with IFN-K using the British Isles Lupus Assessment Group (BILAG)-based Composite Lupus Assessment (BICLA) response criteria. The following assumptions were made for the sample size calculation:

- The error probability for a 2-sided t-test should not exceed 5%;
- The power should be 80% or higher;
- The change of the expression of IFN-induced genes in patients treated with IFN-K is assumed to be -22.6% (data from study IFN-K-001, Lauwerys *et al.*, 2013);
- The change of the expression of IFN-induced genes in patients treated with placebo is assumed to be 10% (data from study IFN-K-001, Lauwerys *et al.*, 2013);
- The common standard deviation of the change is 68 (data from study IFN-K-001, Lauwerys *et al.*, 2013).

The assumptions for the change in expression of IFN gene signature and the standard deviation are based on the original data of study IFN-K-001 as presented in Lauwerys *et al.*, 2013.

With 80 evaluable patients per group i.e. a total of 160 evaluable patients, the study will have a power of 85% to detect a difference of 32.6% in the expression of IFN-induced genes in patients treated with IFN-K compared to patients treated with placebo, assuming that the common standard deviation is 68% and using a two group t-test with a 0.050 two-sided significance level.

[figure not shown]
Assuming a rate of 10% drop-out patients, 178 patients should be enrolled in order to have 160 evaluable patients at Week 36 (80 evaluable patients in each treatment arm=90% of the enrolled patients).

Figure 1 shows – as a sensitivity analysis for the sample size calculation - the number of patients requested for analysis for different assumptions for differences in mean values and standard deviation in the sample size calculation. An increase in the difference of mean values of 5% would

decrease the number of required patients by approximately $n=40$, whereas a decrease in mean differences would increase the required sample size by $n=60$. A decrease in the standard deviation of 8 - at the reference point of 30% mean difference – would decrease the sample size by approximately $n=36$, whereas an increase of 8 would increase the required sample size by approximately $n=38$.

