Taking into account, that the number of patients will be considerable higher in this trial than in the study IFN-K-001, there is a high probability of a smaller standard deviation that could compensate for a possible smaller difference in mean changes. Therefore the sample size calculation gives a realistic estimate of the patients required for analysis to show a significant difference between active treatment and placebo.

Figure 1: Sample-size for different values of between group differences (expression of IFN-induced genes)

[figure not shown]
Assuming common SD=68 and a 0.05 two-sided type-one error rate

Assuming a BICLA response of 20.6% in the placebo group and 40.6% in IFN-K treated patients (i.e. an absolute difference of 20%) with 80 evaluable patients per group, there will be a 73% power to detect a difference of 20% in the BICLA response criterion.

The sample size needed to ensure a 80% power to the comparison of BICLA response rates between IFN-K and placebo for different response rates in the placebo arm and varying between

groups differences are presented in Figure 2. 97 evaluable patients per group would be needed for a power of 80% to detect a difference of 20% with a placebo response rate of 20.6%.

Figure 2: Sample-size for different values of between group differences (BICLA Response rate)

Assuming a power of 80% and a 0.05 two-sided type-one error rate

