2.3.2 Determination of sample size

The primary objective of this study is to evaluate the neutralization of the IFN gene signature following treatment with IFN-K, as measured by the change from baseline of the expression of IFN-induced genes **and** to evaluate the efficacy of treatment with IFN-K using the British Isles Lupus Assessment Group (BILAG)-based Composite Lupus Assessment (BICLA) response criteria. The following assumptions were made for the sample size calculation:

- The error probability for a 2-sided t-test should not exceed 5%;
- The power should be 80% or higher;
- The change of the expression of IFN-induced genes in patients treated with IFN-K is assumed to be -22.6% (data from study IFN-K-001, Lauwers et al., 2013);
- The change of the expression of IFN-induced genes in patients treated with placebo is assumed to be 10% (data from study IFN-K-001, Lauwers et al., 2013);
- The common standard deviation of the change is 68 (data from study IFN-K-001, Lauwers et al., 2013).

The assumptions for the change in expression of IFN gene signature and the standard deviation are based on the original data of study IFN-K-001 as presented in Lauwers *et al.*, 2013.

With 80 evaluable patients per group i.e. a total of 160 evaluable patients, the study will have a power of 85% to detect a difference of 32.6% in the expression of IFN-induced genes in patients treated with IFN-K compared to patients treated with placebo, assuming that the common standard deviation is 68% and using

Statistical Analysis Plan

Study Name: IFN-K-002

SAP version & date: v4, 18/Jun/2018

a two group t-test with a 0.050 two-sided significance level. Assuming a rate of 10% drop-out patients, 178 patients should be enrolled in order to have 160 evaluable patients at Week 36 (80 evaluable patients in each treatment arm=90% of the enrolled patients).

Assuming a BICLA response of 20.6% in the placebo group and 40.6% in IFN-K treated patients (i.e. an absolute difference of 20%) with 80 evaluable patients per group, there will be a 73% power to detect a difference of 20% in the BICLA response criterion.

The sample size needed to ensure a 80% power to the comparison of BICLA response rates between IFN-K and placebo for different response rates in the placebo arm and varying between groups differences are presented in Figure 2 of the protocol. 97 evaluable patients per group would be needed for a power of 80% to detect a difference of 20% with a placebo response rate of 20.6%.

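### Protocol Section 9.2 gives an enrolment total of 166, but every other statement of the target, and the sample-size arithmetic, gives 178

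*Protocol*

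**What the plan says.** Protocol 9.2 (Treatment Allocation and Randomization) reads: "A total of 166 patients will be enrolled in the study and randomly assigned into each cohort sequentially in a 1:1 ratio". It then adds: "Randomized patients who do not receive any study product will not be replaced and will be handled as drop-out patients".

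Five other places in current text give a different total:

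- Protocol synopsis, Study Design: "A total of 178 patients (89 patients in each group) will be enrolled".
- Protocol synopsis, Statistical Design and Sample Size: 178, to give 160 evaluable.
- Protocol 8.1: "The target number of eligible patients to be enrolled in this study is 178 (89 patients in each treatment group").
- Protocol 13.1: "178 patients should be enrolled in order to have 160 evaluable patients at Week 36".
- SAP 2.3.2: "Assuming a rate of 10% drop-out patients, 178 patients should be enrolled in order to have 160 evaluable patients at Week 36".

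On power, Protocol 13.1 sets the requirement that "The power should be 80% or higher" and claims 85% for the IFN gene signature with 80 evaluable per group. For BICLA at the same size it says "there will be a 73% power to detect a difference of 20% in the BICLA response criterion".

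**The concern.** The protocol carries two enrolment targets, and the unsupported one is in the section that leads into treatment supply (9.2.1) and IWRS randomisation (9.2.2). Neither subsection states a total, so 166 is the only patient number in the allocation section. Someone configuring the IWRS or the kit supply from Section 9.2 alone would plan for 12 patients too few.

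If that happened, the trial would miss the 160 evaluable patients on which both power statements rest. The IFN endpoint has some margin over the 80% requirement. BICLA has none: its stated power is already below 80%, and it enters the rule for declaring the study positive. Even if 166 was never used, the protocol does not let a reader decide whether stopping at 166 or continuing to 178 is the compliant course.

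**Working it through.** **Inputs** (Protocol 13.1, repeated in SAP 2.3.2): 80 evaluable per group, 160 in total; dropout 10%; IFN change −22.6% against +10%, a difference of 32.6; common SD 68; two-sided 5% two-group t-test; BICLA response 20.6% against 40.6%. Allocation is 1:1.

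**1. Reproduce the plan's figures.**

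- Enrolment: N = 160/(1 − 0.10) = 177.8, rounded up to 178 (89 per group). Check: 178 × 0.90 = 160.2.
- IFN power: noncentral t with noncentrality (32.6/68) × √(n/2) and 2n − 2 degrees of freedom. At n = 80 the noncentrality is 3.03 and the power 85.4%, against the stated 85%.

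Both reproduce.

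**2. Can 166 be reached?** Multiplying instead of dividing gives 160 × 1.10 = 176, which is not 166 either. Obtaining 160 evaluable from 166 requires dropout of at most 1 − 160/166 = 3.6% (6 patients). No section derives 166.

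**3. What 166 yields at 10% dropout.** 166 × 0.90 = 149.4 evaluable, or 74.7 per group. That is 12 fewer enrolled and about 11 fewer evaluable (160.2 − 149.4 = 10.8).

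**4. IFN power** (difference 32.6, SD 68):

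| Per group | Power |
|---|---|
| 70 | 80.4% |
| 74 | 82.6% |
| 75 | 83.1% |
| 80 | 85.4% |
| 83 | 86.7% |
| 89 | 88.9% |

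The loss is 85.4 − 83.1 = 2.3 to 85.4 − 82.6 = 2.8 points. The 80% requirement is met from 70 per group.

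Protocol 13.8 lets a Visit 9 value stand in for Visit 12, so more than 90% of patients may contribute to this endpoint. If all did, the like-for-like comparison is 83 per group (86.7%) with 89 per group (88.9%), a loss of 2.2 points.

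**5. BICLA power** (20.6% against 40.6%). The documents do not name the method, so three are shown. The continuity-corrected normal approximation, with p̄ = 0.306, is

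Φ{ [0.20 − 1/n − 1.96 √(2p̄(1−p̄)/n)] / √[(0.206×0.794 + 0.406×0.594)/n] }.

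At n = 80 this is Φ{(0.1875 − 0.1428)/0.0711} = Φ(0.628) = 73.5%.

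| Method | n = 74 | n = 75 | n = 80 |
|---|---|---|---|
| Continuity-corrected normal | 69.6% | 70.3% | 73.5% |
| Fisher, exact enumeration | 69.9% | 70.8% | 74.1% |
| Uncorrected Pearson, exact enumeration | 76.4% | 76.3% | 79.6% |

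The first two come close to the stated 73% at 80 per group. Within each method the loss is about 3 to 4 points.

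**The case against.** The strongest reply is that the intended number is not in doubt. The section whose purpose is to set the target, the derivation, the synopsis and the later SAP all say 178. The Amendment #3 rationale (Protocol 5.8) says that the sample-size calculation was revised, so 166 is most simply a leftover. Nothing suggests that it was implemented. Even if it was, IFN power stays above 80%, and the hypotheses, tests and decision rule are untouched. This stands as a limit on the consequence. It does not remove the contradiction, and the documents confirm neither the origin of 166 nor which number was configured.

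Three narrower points also stand:

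- Non-replacement of undosed patients applies equally to 178. Because they count as drop-outs, they can sit within the 10% allowance. The rule shows only that no top-up bridges 166 and 178.
- The BICLA figures are indicative. The continuity-corrected formula that comes near 73% at 80 per group gives 82.4% at 97 per group, where Protocol 13.1 and SAP 2.3.2 say 97 are needed for 80%. It does not reproduce both published figures.
- The documents' own arithmetic is sound. The fault is one figure inconsistent with it.

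A distinction between enrolled and randomised patients does not help: the synopsis and Section 8.1 also speak of enrolment and split 178 into 89 per group.

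**Conclusion.** The point holds. Section 9.2 is current operative text, its total conflicts with five other statements, and only 178 follows from 160 evaluable patients at 10% dropout. It should be corrected, but it does not threaten the trial's validity.

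If 166 was implemented and dropout was 10%, the cost is about 11 evaluable patients, 2 to 3 points of IFN power and roughly 3 to 4 points of BICLA power. These sizes rest on the protocol's planning assumptions and, for BICLA, on an unidentified power method. If 178 was implemented, there is no loss and the defect is confined to the text.

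**What to change.** In Protocol 9.2, replace 166 by 178 (89 per group). In the same edit, remove the reference to sequential assignment into cohorts: the design has two parallel groups allocated by central minimisation. That second change is editorial, with no shown effect on allocation.

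Then confirm that any enrolment cap in the IWRS and the kit supply used 178. SAP version 4, dated 18 June 2018, already describes randomised patients at 65 sites, so this check may be retrospective. In that case, record which total was applied.

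The cost is one line of protocol text and a check of two settings. No patients are added to the stated target.

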9.2.1 Treatment Supply

A packaging list will be computer-generated using a standard Statistical Analysis System (SAS)® program and will be used to number the treatment kits.

IFN-K and placebo treatment kits will be distributed to each Investigational site.

9.2.2 Randomization of Patients

Treatment allocation at each site will be performed using central randomization via an Interactive Web Response System (IWRS). The randomization algorithm was developed using a stochastic minimization with a minimization probability parameter of 0.80. Randomization will be minimized by:

- Ethnic Origin: Black, Asian, Caucasian/Hispanic, other
- Age: 18-40 & 41-65 years old
- Presence or absence of renal BILAG at screening
- With or without CS treatment at randomization
- With or without HCQ treatment at randomization
- With or without MMF treatment at randomization

At the time of randomization, the IWRS will assign the patient to a treatment arm and will provide the number of the treatment kit for the first injection. The actual treatment numbers administered to the patient will be recorded in the eCRF.

Please refer to Section 10.1 for details about patient identification.

10. STUDY PROCEDURES

10.1 Patient Identification

Patients will be screened for eligibility for the study. The identification number will consist of six digits (two digits to represent the country, two to represent the site, and two to represent the patient's order of inclusion at the site).

Patients will be identified by their unique identification number throughout the study.

10.2 Method of Blinding and Breaking the Study Blind

10.2.1 Blinding rules

The study will be conducted with a double-blind design (patient and investigator will be blinded). As the placebo is not identical to the IFN-K, blinding rules will be set up and maintained during the whole study:

Treatment

The injected study product is an emulsion indistinguishable whether it has been prepared with IFN-K or placebo.

The pharmacist or the authorized designated person in charge of study product preparation will prepare the emulsion and deliver the blinded ready to use syringes in order that neither the patient nor the investigator will know the allocated treatment. He/she will be the only person knowing treatment allocation during the whole study.

The randomization list is centralized and treatment allocation will be through IWRS. At randomization and at each treatment visit, a blinded kit number is allocated to the patient.

Outcome used to evaluate endpoints

IFN gene signature, assessed as primary endpoint will be performed blind on anonymized samples, by a central specialized laboratory *a posteriori* when the patient will have completed the study. Procedures for assessment of immunogenicity (secondary endpoints) will be identical.

An independent adjudication committee will review and validate the BILAG on blinded data for consistency in the scoring.

Laboratory results will not be expected to reveal the treatment allocation.

Monitoring and study product accountability

Monitoring visits at pharmacy will be performed by an unblinded CRA who is different from the site designated CRA. Drug accountability will be performed at regular interval and potential issues/discrepancies will be reported in a separate « monitoring report » sent to reviewer independent from the Sponsor or a contractor involved in the study.

During the monitoring visit on site, the allocated treatment group will remain blinded for the site designated CRA.

10.2.2 Unblinding procedure

If knowledge of the study product (IFN-K or placebo) is necessary for optimal emergency treatment, the Investigator may break the treatment code through the IWRS. If possible, the Neovacs SA Clinical Safety Physician or Delegate Medical Monitor assigned to the investigational site should be consulted before breaking the study blind. In case of pregnancy, the investigator will be asked to break the treatment code and inform Neovacs SA Clinical Safety physician. The investigator will also have to notify the Pharmacovigilance Department of the contracted CRO by filling the Pregnancy form.

In any case, the Investigator must record the reason for breaking the study blind in the eCRF, and the site designated CRA must be notified as soon as possible.

Neovacs Clinical Safety Physician

[contact]

[contact]

Mobile phones for 7/7 day availability: [name]

Medical Monitor

Mobile phone for 7/7 day availability: [name]

10.3 Independent Data and Safety Monitoring Board

An iDSMB consisting of experts in the appropriate disciplines will ensure the safety of participating patients. The role and responsibilities of the iDSMB, as well as the data review process are outlined in detail in a separate iDSMB Charter.

In addition to planned iDSMB reviews, unscheduled meeting may be triggered in case of emerging safety concerns. Specifically, unscheduled meetings may be called at the request of any iDSMB member, the Study Chairman, or the Sponsor at any time during the study. The iDSMB will meet if any of the following occur during the study:

- A death or a medically significant and immediately life-threatening condition is sustained by one patient enrolled in the study, regardless of the study treatment causality;
- Two consecutive treatment-related SAEs;
- An unanticipated significant safety issue is newly identified during the development program of IFN-K that could expose treated patients to unnecessary risk;
- Any other concern regarding patient safety raised by any iDSMB member, the Study Chairman, or the Sponsor at any time during the study.

The available safety, immune responses and clinical data will be reviewed by the iDSMB through ad-hoc meetings. Rules for reviewing data will be described in the charter. iDSMB may recommend an amendment to the study protocol, or premature termination of the study. Such iDSMB recommendations will be submitted to the Sponsor. If applicable, they will be submitted to Independent Ethics Committees (IECs) and Competent Authorities.

